## Micellar Cleanser

207782

Draft Statistical Reporting and Analysis plan Amendment #1, 14 Aug 2017

	Micellar Cleanser (N=xx)	Micellar Foaming Cleanser (N=xx)	Overall (N=xx)
SEX n (%)			
FEMALE	XX (XX.X)	XX (XX.X)	XX (XX.X)
RACE n (%)			
AFRICAN AMERICAN/AFRICAN HERITAGE	XX (XX.X)	XX (XX.X)	XX (XX.X)
AMERICAN INDIAN OR ALASKAN NATIVE	XX (XX.X)	XX (XX.X)	XX (XX.X)
ASIAN - CENTRAL/SOUTH ASIAN HERITAGE	XX (XX.X)	XX (XX.X)	XX (XX.X)
ASIAN - JAPANESE HERITAGE			
ASIAN - EAST ASIAN HERITAGE	XX (XX.X)	XX (XX.X)	XX (XX.X)
ASIAN - SOUTH EAST ASIAN HERITAGE	XX (XX.X)	XX (XX.X)	XX (XX.X)
NATIVE HAWAIIAN OR OTHER PACIFIC ISLANDER	XX (XX.X)	XX (XX.X)	XX (XX.X)
WHITE - ARABIC/NORTH AFRICAN HERITAGE	XX (XX.X)	XX (XX.X)	XX (XX.X)
WHITE - WHITE/CAUCASIAN/EUROPEAN HERITAGE	XX (XX.X)	XX (XX.X)	XX (XX.X)
AGE (YEARS)			
n	XX	XX	XX
MEAN	XX.X	XX.X	XX.X
SD	XX.XX	XX.XX	XX.XX
MEDIAN	XX.X	XX.X	XX.X
MINIMUM	XX	XX	XX
MAXIMUM	XX	XX	XX
CONTACT LENS WEARER			
YES	XX (XX.X)	XX (XX.X)	XX (XX.X)
NO	XX (XX.X)	XX (XX.X)	XX (XX.X)
FITZPATRICK SKIN TYPE n (%)			
I	XX (XX.X)	XX (XX.X)	XX (XX.X)
II	XX (XX.X)	XX (XX.X)	XX (XX.X)
III	XX (XX.X)	XX (XX.X)	XX (XX.X)
IV	XX (XX.X)	XX (XX.X)	XX (XX.X)
V	XX (XX.X)	XX (XX.X)	XX (XX.X)

Micellar Cleanser

207782

Draft Statistical Reporting and Analysis plan Amendment #1, 14 Aug 2017

---

VI	XX (XX.X)	XX (XX.X)	XX (XX.X)
COSMETIC SKIN TYPE n (%)			
DRY	XX (XX.X)	XX (XX.X)	XX (XX.X)
NORMAL/COMBINATION	XX (XX.X)	XX (XX.X)	XX (XX.X)

PPD

Page X of Y

Micellar Cleanser

207782

Draft Statistical Reporting and Analysis plan Amendment #1, 14 Aug 2017

Protocol: 207782

Program Run Date: ddmonyyyy

Table 14.2.1.1  
Frequency of Combined Dermatologist and Ophthalmologist Score  
Intent to Treat Population

Intent to Treat Population (N=XX)				
Timepoint	Micellar Cleanser		Micellar Foaming Cleanser	
	Combined Dermatologist and Ophthalmologist Score	(N=XX)	(N=XX)	n (%)
BASELINE				
0	xx (xx.xx)		xx (xx.xx)	
1	xx (xx.xx)		xx (xx.xx)	
2	xx (xx.xx)		xx (xx.xx)	
...	xx (xx.xx)		xx (xx.xx)	
16	xx (xx.xx)		xx (xx.xx)	
1 HOUR				
0	xx (xx.xx)		xx (xx.xx)	
1	xx (xx.xx)		xx (xx.xx)	
2	xx (xx.xx)		xx (xx.xx)	
...	xx (xx.xx)		xx (xx.xx)	
16	xx (xx.xx)		xx (xx.xx)	
DAY 21#				
0	xx (xx.xx)		xx (xx.xx)	
1	xx (xx.xx)		xx (xx.xx)	
2	xx (xx.xx)		xx (xx.xx)	
...	xx (xx.xx)		xx (xx.xx)	
16	xx (xx.xx)		xx (xx.xx)	
SUM OF POST-BASELINE COMBINED DERMATOLOGIST AND OPHTHALMOLOGIST SCORES				
0	xx (xx.xx)		xx (xx.xx)	
1	xx (xx.xx)		xx (xx.xx)	
2	xx (xx.xx)		xx (xx.xx)	
...	xx (xx.xx)		xx (xx.xx)	
32	xx (xx.xx)		xx (xx.xx)	

Combined dermatologist and ophthalmologist score = dermal response score + superficial irritation score + conjunctive involvement score + lacrimal intensity score

# Primary endpoint is at Day 21.

Micellar Cleanser

207782

Draft Statistical Reporting and Analysis plan Amendment #1, 14 Aug 2017

---

PPD

**Programming Note:**

- This shell is used for tables 14.2.1.2, 14.2.2.1, 14.2.2.2, 14.2.4.1, 14.2.4.2 14.2.7.1 and 14.2.7.2. Replace the formula in the footnote with the correct applicable formula. For the tables by strata add "Strata: NOT contact lens wearer with Dry skin" etc. below the line "Intent to Treat Population (N=XX)". Remove # footnote for all other tables.

Page X of Y

Micellar Cleanser

207782

Draft Statistical Reporting and Analysis plan Amendment #1, 14 Aug 2017

Protocol: 207782

Program Run Date: ddmonyyyy

Table 14.2.5.1  
Frequency of Dermal Response Score  
Intent to Treat Population

Intent to Treat Population (N=XX)

Timepoint	Micellar Cleanser (N=XX)	Micellar Foaming Cleanser (N=XX)
	n (%)	n (%)
BASELINE		
0	xx (xx.xx)	xx (xx.xx)
1	xx (xx.xx)	xx (xx.xx)
2	xx (xx.xx)	xx (xx.xx)
...	xx (xx.xx)	xx (xx.xx)
7	xx (xx.xx)	xx (xx.xx)
1 HOUR		
0	xx (xx.xx)	xx
1	xx (xx.xx)	xx
2	xx (xx.xx)	xx
...	xx (xx.xx)	xx
7	xx (xx.xx)	xx
DAY 21		
0	xx (xx.xx)	xx (xx.xx)
1	xx (xx.xx)	xx (xx.xx)
2	xx (xx.xx)	xx (xx.xx)
...	xx (xx.xx)	xx (xx.xx)
SUM OF POST-BASELINE DERMAL RESPONSE SCORES		
.....	xx (xx.xx)	xx (xx.xx)

0 = No evidence of irritation; 1= Minimal erythema barely perceptible; 2 = Definite erythema; readily visible;or minimal edema; minimal popular response; 3 = Erythema and papules;4 = Definite edema; 5 = Erythema, edema and papules; 6 = Vesicular eruption; 7 = Strong reaction spreading beyond test site.

PPD

Page X of Y

Micellar Cleanser

207782

Draft Statistical Reporting and Analysis plan Amendment #1, 14 Aug 2017

---

**Programming Note:**

- This shell is used for tables 14.2.3.2, 14.2.6.1 and 14.2.6.2. Replace the score decode footnote with the corresponding footnote. For the tables by strata add "Strata: NOT contact lens wearer with Dry skin" etc. below the line "Intent to Treat Population (N=XX)".

Micellar Cleanser

207782

Draft Statistical Reporting and Analysis plan Amendment #1, 14 Aug 2017

Protocol: 207782

Program Run Date:ddmonyyyy

Table 14.2.6.1  
Frequency of Conjunctiva Involvement Score  
Intent to Treat Population

Intent to Treat Population (N=XX)

Timepoint	Micellar Cleanser (N=XX)	Micellar Foaming Cleanser (N=XX)
Conjunctiva Involvement Score/Grade	n (%)	n (%)
BASELINE		
0/NONE	xx (xx.xx)	xx (xx.xx)
1/MILD	xx (xx.xx)	xx (xx.xx)
2/MODERATE	xx (xx.xx)	xx (xx.xx)
3/SEVERE	xx (xx.xx)	xx (xx.xx)
1 HOUR		
0/NONE	xx (xx.xx)	xx (xx.xx)
1/MILD	xx (xx.xx)	xx (xx.xx)
2/MODERATE	xx (xx.xx)	xx (xx.xx)
3/SEVERE	xx (xx.xx)	xx (xx.xx)
DAY 21		
0/NONE	xx (xx.xx)	xx (xx.xx)
1/MILD	xx (xx.xx)	xx (xx.xx)
2/MODERATE	xx (xx.xx)	xx (xx.xx)
3/SEVERE	xx (xx.xx)	xx (xx.xx)
SUM OF POST-BASELINE CONJUNCTIVA INVOLVEMENT SCORES		
.....	xx (xx.xx)	xx (xx.xx)

None = No involvement; Mild = Conjunctivae (palpebral and bulbar) injected above normal with possible chemosis (swelling); no discharge; Moderate = Conjunctivae injected above normal; obvious swelling; possible discharge; Severe = Conjunctivae more diffuse, deeper crimson red, individual vessels not easily discernible; excessive swelling and/or discharge

PPD

Page X of Y

**Programming Note:**

Micellar Cleanser

207782

Draft Statistical Reporting and Analysis plan Amendment #1, 14 Aug 2017

---

- This table shell is used for Table 14.2.5.2 as well. Add "Strata: NOT contact lens wearer with Dry skin" etc. below the line "Intent to Treat Population (N=XX)".

Micellar Cleanser

207782

Draft Statistical Reporting and Analysis plan Amendment #1, 14 Aug 2017

Protocol: 207782

Program Run Date:ddmonyyyy

Table 14.2.8.1  
Frequency of Subject Assessment Scores for Eyes  
Intent to Treat Population

Intent to Treat Population (N=XX)

Assessment: Redness

Timepoint	Micellar Cleanser	Micellar Foaming Cleanser
	(N=XX)	(N=XX)
	n (%)	n (%)
BASELINE		
0/NONE	xx (xx.xx)	xx (xx.xx)
1/MILD	xx (xx.xx)	xx (xx.xx)
2/MODERATE	xx (xx.xx)	xx (xx.xx)
3/SEVERE	xx (xx.xx)	xx (xx.xx)
1 HOUR		
0/NONE	xx (xx.xx)	xx (xx.xx)
1/MILD	xx (xx.xx)	xx (xx.xx)
2/MODERATE	xx (xx.xx)	xx (xx.xx)
3/SEVERE	xx (xx.xx)	xx (xx.xx)
DAY 21		
0/NONE	xx (xx.xx)	xx (xx.xx)
1/MILD	xx (xx.xx)	xx (xx.xx)
2/MODERATE	xx (xx.xx)	xx (xx.xx)
3/SEVERE	xx (xx.xx)	xx (xx.xx)
SUM OF POST-BASELINE REDNESS SCORES		
.....	xx (xx.xx)	xx (xx.xx)

PPD

Programming Note: Repeat for Dryness, Burning, Itching and Stinging. This shell will also be used for table 14.2.9.1.

Page X of Y

Micellar Cleanser

207782

Draft Statistical Reporting and Analysis plan Amendment #1, 14 Aug 2017

Protocol: 207782

Program Run Date:ddmonyyyy

Table 14.2.8.2  
Frequency of Subject Assessment Combined Score\* for Eyes  
Intent to Treat Population

Intent to Treat Population (N=XX)

Timepoint	Micellar Cleanser	Micellar Foaming Cleanser
	(N=XX)	(N=XX)
	n (%)	n (%)
BASELINE		
0	xx (xx.xx)	xx (xx.xx)
1	xx (xx.xx)	xx (xx.xx)
...	xx (xx.xx)	xx (xx.xx)
15	xx (xx.xx)	xx (xx.xx)
1 HOUR		
0	xx (xx.xx)	xx (xx.xx)
1	xx (xx.xx)	xx (xx.xx)
...	xx (xx.xx)	xx (xx.xx)
15	xx (xx.xx)	xx (xx.xx)
DAY 21		
0	xx (xx.xx)	xx (xx.xx)
1	xx (xx.xx)	xx (xx.xx)
...	xx (xx.xx)	xx (xx.xx)
15	xx (xx.xx)	xx (xx.xx)
SUM OF POST-BASELINE COMBINED SCORE* FOR EYES		
.....	xx (xx.xx)	xx (xx.xx)

\* Combined score for eyes is obtained by summing the 5 subject assessments for eyes i.e. redness, dryness, burning, itching and stinging.

PPD

Programming Note:This shell will also be used for table 14.2.9.2 (same footnote applies).

Page X of Y

Micellar Cleanser

207782

Draft Statistical Reporting and Analysis plan Amendment #1, 14 Aug 2017

Protocol: 207782

Program Run Date: ddmmmyyyy

Table 14.3.1.1  
Treatment Emergent Adverse Events by System Organ Class and Preferred Term  
Safety Population

System Organ Class Preferred Term	Micellar Cleanser (N=xx)		Micellar Foaming Cleanser (N=xx)		Overall (N=xx)	
	n (%)	nAE	n (%)	nAE	n (%)	nAE
NUMBER OF SUBJECTS WITH AT LEAST ONE AE	xx (xx.x)		xx (xx.x)		xx (xx.x)	
NUMBER OF SUBJECTS WITH NO AE	xx (xx.x)		xx (xx.x)		xx (xx.x)	
AUTONOMIC NERVOUS SYSTEM	x (x.x)	x	x	x	x	x
MOUTH DRY	x (x.x)	x	x	x	x	x
BODY AS A WHOLE GENERAL	x (x.x)	x	x	x	x	x
PAIN	x (x.x)	x	x	x	x	x
CENTRAL AND PERIPHERAL NERVOUS SYSTEM	x (x.x)	x	x (x.x)	x	x (x.x)	x
DIZZINESS	x	x	x (x.x)	x	x	x
HEADACHE	x (x.x)	x	x	x	x (x.x)	x
GASTROINTESTINAL SYSTEM	x	x	x	x	x (x.x)	x
ABDOMINAL PAIN	x	x	x	x	x	x
ANOREXIA	x	x	x	x	x (x.x)	x
VOMITING	x	x	x	x	x	x

n (%) = Number (percent) of subjects.

nAE = Number of Adverse Events.

PPD

Page x of y

Micellar Cleanser

207782

Draft Statistical Reporting and Analysis plan Amendment #1, 14 Aug 2017

Protocol: 207782

Program Run Date: ddmmmyyyy

Table 14.3.1.2  
Treatment Emergent Adverse Events by System Organ Class, Preferred Term and Severity  
Safety Population

System Organ Class Preferred Term	Micellar Cleanser (N = XX)			Micellar Foaming Cleanser (N = XX)		
	n	(%)	nAE	n	(%)	nAE
Mild	Moderate	Severe	Mild	Moderate	Severe	
Any TEAE	xx (xx.x) xx	xx (xx.x) xx	xx (xx.x) xx	xx (xx.x) xx	xx (xx.x) xx	xx (xx.x) xx
Nervous system disorders	xx (xx.x) xx	xx (xx.x) xx	xx (xx.x) xx	xx (xx.x) xx	xx (xx.x) xx	xx (xx.x) xx
Headache	xx (xx.x) xx	xx (xx.x) xx	xx (xx.x) xx	xx (xx.x) xx	xx (xx.x) xx	xx (xx.x) xx
Dizziness	xx (xx.x) xx	xx (xx.x) xx	xx (xx.x) xx	xx (xx.x) xx	xx (xx.x) xx	xx (xx.x) xx
Respiratory, thoracic and mediastinal disorders	xx (xx.x) xx	xx (xx.x) xx	xx (xx.x) xx	xx (xx.x) xx	xx (xx.x) xx	xx (xx.x) xx
Nasal mucosal erosion	xx (xx.x) xx	xx (xx.x) xx	xx (xx.x) xx	xx (xx.x) xx	xx (xx.x) xx	xx (xx.x) xx
Nasal congestion	xx (xx.x) xx	xx (xx.x) xx	xx (xx.x) xx	xx (xx.x) xx	xx (xx.x) xx	xx (xx.x) xx
Nasal discomfort	xx (xx.x) xx	xx (xx.x) xx	xx (xx.x) xx	xx (xx.x) xx	xx (xx.x) xx	xx (xx.x) xx

n (%) = Number (percent) of subjects.

nAE = Number of Adverse Events.

Page x of y

PPD

Protocol: 207782

Program Run Date: DDMMYYYY

Micellar Cleanser

207782

Draft Statistical Reporting and Analysis plan Amendment #1, 14 Aug 2017

---

Listing 16.1.7  
Randomization Information  
All Randomized Subjects

Study Population: Randomised Subjects (N=xxx)

Stratum: Not contact lens wearer with dry skin

Subject	Randomisation Number	Treatment	Randomisation Date
PPD		MICELLAR CLEANSER MICELLAR FOAMING CLEANSER	DDMMYYYY DDMMYYYY
...			

PPD

Page x of y

Micellar Cleanser

207782

Draft Statistical Reporting and Analysis plan Amendment #1, 14 Aug 2017

---

Protocol: 207782

Program Run Date: DDMMYYYY

Listing 16.2.1.1  
Subject Disposition  
All Screened Subjects

Subject	Sex/Age/ Race [1]	Screening date	Treatment Start Date and Time	Date of Completion or withdrawal	Duration of Treatment (Days)	Completed (Yes/No)	Randomized (Yes/No)	Primary Reason for Withdrawal
PPD								

...  
[1] Age in years; Sex: F = Female, M = Male; Race: A = Asian, B = Black or African American, I = American Indian or Alaska Native, H = Native Hawaiian or Other Pacific Islander, W = White, M = Multiple.

PPD

Page x of y

Micellar Cleanser

207782

Draft Statistical Reporting and Analysis plan Amendment #1, 14 Aug 2017

---

Protocol: 207782

Program Run Date: DDMMYYYY

Listing 16.2.2  
Individual Subjects Protocol Violation  
All Randomised Subjects

Treatment Group: Micellar Cleanser

Subject	Age/Sex/Race[1]	Visit	Violation Sequence	Protocol Violation
PPD				xxxxxxxxxxxxxxxxxxxxxxxxxxxxxxxxxxxxxx

[1] Age in years; Sex: F = Female, M = Male ; Race: A = Asian, B = Black or African American, I = American Indian or Alaska Native, H = Native Hawaiian or Other Pacific Islander, W = White, O = Multiple.

PPD

Page x of y

Micellar Cleanser

207782

Draft Statistical Reporting and Analysis plan Amendment #1, 14 Aug 2017

---

Protocol: 207782

Program Run Date: DDMMYYYY

**Listing 16.2.3.1**  
Exclusions from Analysis Populations  
All Randomized Subjects

Treatment Group: Micellar Cleanser

Subject	Sex/Age/ Race [1]	Treatment Start Date and Time	Safety (Yes/No)	Intent To Treat (Yes/No)
PPD			No	No
...				

[1] Age in years; Sex: F = Female, M = Male; Race: A = Asian, B = Black or African American, I = American Indian or Alaska Native, H = Native Hawaiian or Other Pacific Islander, W = White, M = Multiple.

PPD

Page x of y

Micellar Cleanser

207782

Draft Statistical Reporting and Analysis plan Amendment #1, 14 Aug 2017

---

Protocol: 207782

Program Run Date: DDMMYYYY

**Listing 16.2.4.1**  
Demographic Characteristics  
All Randomized Subjects

Treatment Group: Micellar Cleanser

Subject	Sex	Race	Age (years)	Contact Lens Wearer (Yes/No)	Fitzpatrick Skin Type	Cosmetic Skin Type
PPD						
...						

PPD

Page x of y

Micellar Cleanser

207782

Draft Statistical Reporting and Analysis plan Amendment #1, 14 Aug 2017

---

Protocol: 207782

Program Run Date: DDMMYYYY

Listing 16.2.4.2  
Medical History  
All Randomized Subjects

Treatment Group: Micellar Cleanser

Subject	Sex/Age/ Race [1]	Any Medical History? (Yes/No)	Medical Condition	Start Date	Ongoing? (Yes/No)	End Date
PPD			xxxxxxxxxxxx	DDMMYYYY	No	DDMMYYYY

....  
[1] Age in years; Sex: F = Female, M = Male; Race: A = Asian, B = Black or African American, I = American Indian or Alaska Native, H = Native Hawaiian or Other Pacific Islander, W = White, M = Multiple.

PPD

Page x of y

Micellar Cleanser

207782

Draft Statistical Reporting and Analysis plan Amendment #1, 14 Aug 2017

Protocol: 207782

Program Run Date: DDMMYYYY

Listing 16.2.6.1  
Dermatologist and Ophthalmologist Scores  
All Randomized Subjects

Treatment Group: Micellar Cleanser

Subject	Sex/Age/ Race [1]	Visit	Visit Date	Dermal Response Score [2]	Superficial Irritation Score [3]	Combined Dermatologist Score	Conjunctiva Involvement (Score) [4]	Lacrimal Intensity (Score) [5]	Combined Ophthalmologist Score	Combined Dermatologist and Ophthalmologist Score (modified)
PPD										
<hr/>										

[1] Age in years; Sex: F = Female, M = Male; Race: A = Asian, B = Black or African American, I = American Indian or Alaska Native, H = Native Hawaiian or Other Pacific Islander, W = White, M = Multiple.

[2] 0 = No evidence of irritation; 1 = Minimal erythema; barely perceptible; 2 = Definite erythema, readily visible or minimal edema or minimal popular response; 3 = Erythema and papules; 4 = Definite edema; 5 = Erythema, edema and papules; 6 = Vesicular eruption; 7 = Strong reaction spreading beyond test site.

[3] A(0) = Slight glazed appearance; B(1) = Marked glazing; C(2) = Glazing with peeling and cracking; F(3) Glazing and fissures; G(3) = Film of dried serous exudate covering all or portion of the patch; H(3) = Small petechial erosions and/or scabs.

[4] 0 = None - No involvement; 1 = Mild - Conjunctivae (palpebral and bulbar) injected above normal with possible chemosis (swelling), no discharge; 2 = Moderate - Conjunctivae injected above normal, obvious swelling, possible discharge; 3 = Severe - Conjunctivae more diffuse, deeper crimson red, individual vessels not easily discernible, excessive swelling and/or discharge.

[5] 0 = None - No lacrimal observation; 1 = Mild - Excessive wetness (no distinct tears); 2 = Moderate - A few formed tears (contained in orbit); 3 = Severe - Intense tearing (leaving orbit).

Combined Dermatologist and Ophthalmologist Score = Combined Dermatologist Score + Combined Ophthalmologist Score.

Combined Dermatologist and Ophthalmologist Score (modified) = Dermal Response Score + Conjunctiva Involvement Score + Lacrimal Intensity Score.

Page x of y

PPD

**Programming Note: Please include the sum of post baseline scores.**

Micellar Cleanser

207782

Draft Statistical Reporting and Analysis plan Amendment #1, 14 Aug 2017

---

Protocol: 207782

Program Run Date: DDMMYYYY

Listing 16.2.6.2.1  
Subject Self-Assessment (Face)  
All Randomised Subjects

Treatment Group: Micellar Cleanser

Subject	Sex/Age/ Race [1]	Visit	Visit Date	Redness	Dryness	Burning	Itching	Stinging	Combined Score
PPD									
...									

[1] Age in years; Sex: F = Female, M = Male; Race: A = Asian, B = Black or African American, I = American Indian or Alaska Native, H = Native Hawaiian or Other Pacific Islander, W = White, M = Multiple.

Page x of y

PPD

Programming Note: Please include the sum of post baseline scores.

Micellar Cleanser

207782

Draft Statistical Reporting and Analysis plan Amendment #1, 14 Aug 2017

---

Protocol: 207782

Program Run Date: DDMMYYYY

Listing 16.2.6.2.2  
Subject Self-Assessment (Eye)  
All Randomised Subjects

Treatment Group: Micellar Cleanser

Subject	Sex/Age/ Race [1]	Visit	Visit Date	Redness	Dryness	Burning	Itching	Stinging	Combined Score
PPD									

[1] Age in years; Sex: F = Female, M = Male; Race: A = Asian, B = Black or African American, I = American Indian or Alaska Native, H = Native Hawaiian or Other Pacific Islander, W = White, M = Multiple.

PPD

Page x of y

Programming Note: Please include the sum of post baseline scores.

Micellar Cleanser

207782

Draft Statistical Reporting and Analysis plan Amendment #1, 14 Aug 2017

Protocol: 207782

Program Run Date: DDMMYYYY

Listing 16.2.7.1

All Adverse Events

All Randomized Subjects

Treatment Group: Micellar Cleanser

Subject	Sex/Age/ Race [1]	Adverse Event (Preferred Term) [System Organ Class]	Start Date (Study Day) [2]	Start Time	End Date	End Time	Frequency/ Intensity [3]	Related to Study Product?	Action Taken Re Study Product	Withdraw?
PPD										
....										

[1] Age in years; Sex: F = Female, M = Male; Race: A = Asian, B = Black or African American, I = American Indian or Alaska Native, H = Native Hawaiian or Other Pacific Islander, W = White, M = Multiple.

[2] Study day is the day relative to start of treatment, day 1 being the day of first treatment.

[3] INT = Intermittent and SGLE = Single.

[4] Did subject withdraw from study as a result of this adverse event?

PPD

Page x of y

**Programming Note:**

- Repeat the same layout for the listing 16.2.7.2
- Population should be used 'Non randomised Subjects'
- The fourth column should be only 'Start Date'
- Delete the footnote related to study day and adjust the numbers accordingly.

## Document History

Document	Version Date	Summary of Changes (New analysis or Change in planned analysis)
Addendum 1	04-Dec-2017	Disposition table includes additional summary for total number of subjects who underwent the lactic acid sting test. Change in the definition of Safety Population Added TEAEs definition for more clarity.
Amendment 1	14-Aug-2017	Added new mandatory listings and incorporated in new template.
Original Analysis Plan	30-Jun-2017	Not applicable (N/A)

## 1 Introduction

This RAP addendum describes the changes, deviations and clarifications to the planned analysis described in the Statistical Reporting and Analysis Plan Amendment 1 and protocol version 2.0. These changes were identified during CSR development, and hence were identified after unblinding but prior to final CSR. These changes will be reflected in the final CSR.

The sections below provide the updated text that are required from the planned analysis, with section 5.0 providing further details on what was planned, the change and the reason for the change. A summary of the changes/clarifications are:

- Number of subjects who underwent the lactic acid sting test: this summary will be added to the disposition table 14.1.1.
- Safety population definition: The definition applied to the tables, figures and listings (TFLs) differed from the planned definition in the RAP amendment and protocol V2.0.
- Treatment emergent adverse event (TEAE) definition: No definition was previously provided; hence a definition has been added for clarity and consistency with the updated safety population definition.
- Update to study duration derivation in Listing 16.2.1.1

### 4.1 Populations for Analysis

#### 4.1.1 Subject Disposition

Screen failures will be defined as subjects who do not satisfy all the inclusion/exclusion criteria. A summary will be provided of the number of subjects screened and the number of screen failures with reasons why subjects were not randomized. Additionally, the number and percentage of subjects who underwent the lactic acid sting test will also be presented ([Table 14.1.1](#)).

Subject disposition will also be summarized as the number and percentage of subjects (out of the number of randomised subjects) who complete the study, with the number who discontinue broken down by reason for discontinuation ([Table 14.1.1](#)). The table will also summarize the number and percent of subjects assigned to each analysis population (refer to section 4.1.3).

Subject disposition including the subject status (completer, Yes/No), critical demographic data (age, sex, race), the duration of treatment [(date of completion or withdrawal - treatment start date)+1] before discontinuation and the specific reason for discontinuation, will be listed in [Listing 16.2.1.1](#), by treatment group.

#### 4.1.3 Analysis Populations

Two analysis populations are defined.

Population	Definition / Criteria	Analyses Evaluated
Safety	
 
• All subjects, for whom the lactic acid stinging test was performed, were randomized and had at least one study treatment application.
 
• This population will be based on the treatment the subject actually received.
 
	
 
• Safety
 

Intent-To-Treat	
 
• Comprises of all randomized subjects who have at least one cutaneous or ocular assessment following study product application.
 
• This population will be based on the treatment the subject is randomised to.
 
	
 
• Efficacy
 

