9.2. General Considerations

9.2.1. Definition of Analysis Populations

The ‘Intent to treat’ (ITT) population includes all subjects who are randomized into the study and have at least one cutaneous or ocular assessment following study product application.

A separate Per Protocol (PP) analysis will not be performed. Protocol deviations will however be listed for review.

The Safety population includes all subjects from the point of the lactic acid stinging test procedure until completion of the study.

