#### 4.1.3 Analysis Populations

Two analysis populations are defined.

Population	Definition / Criteria	Analyses Evaluated
Safety	
 
Comprises of all subjects for whom the lactic acid stinging test was performed.
 
This population will be based on the treatment the subject actually received.
 
	
 
Safety
 

Intent-To-Treat	
 
Comprises of all randomized subjects who have at least one cutaneous or ocular assessment following study product application.
 
This population will be based on the treatment the subject is randomised to.
 
	
 
Efficacy
 

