## 4.6 Analysis of Safety

### 4.6.1 Adverse Events and Serious Adverse Events

Adverse events (AEs) will be captured following the lactic acid stinging test procedure.

All adverse events (AEs) will be summarised by primary system organ class and preferred term according to the current version of the MedDRA.

TEAEs are defined as new AEs that occur on or after the date/time of first supervised treatment product use. Events with an onset date/time prior to the first use of treatment product will be considered as non-treatment emergent.

Treatment emergent adverse events (TEAEs) will be summarized by the number and percentage of subjects having any adverse event, an adverse event in each System Organ Class, and each individual adverse event. All TEAEs will also be tabulated by severity. Treatment-emergent AEs suspected of a relationship to study product will be presented in a similar manner. For treatment-related AEs, these will also be presented by severity.

Deaths occurring during treatment (if any) will be listed by treatment, including the date and study day of death, and the principal cause of death. Serious adverse events leading to discontinuation will be listed. All AEs will be listed.

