**Table 1 Changes to SAP amendment Defined Analysis Plan**

SAP Analysis Plan Amendment 1	Statistical Analysis Plan Addendum	Rationale for Changes

 
1.1.2 Analysis Population The Safety population includes all subjects from the point of the lactic acid stinging test procedure until completion of the study.
 
	
 
1.1.2 Analysis Population All subjects, for whom the lactic acid stinging test was performed, were randomized and had at least one study treatment application.
 
	
It was originally planned to report all AEs from the point of lactic acid sting test as the subjects would have been applied the acid solution to potential subjects in the study. However this sting test was performed at the screening visit and therefore not everyone who had the sting test performed would have been randomised and received treatment product. Therefore some of the AEs reported after the sting test would not have been classified as treatment emergent. During the programming of the AE TFLs for the CSR, it was assumed all subjects in safety population were randomized and received treatment product, hence any AEs from this safety population definition would have been TEAEs (if started after product use). However the safety population definition applied to the TFLs differed from the planned definition. Once this was identified during the CSR development, the study team decided that the definition of the safety population and TEAE definition applied to the TFLs was the most appropriate. Hence change/clarification to the definitions in this RAP addendum.

 
Section 4.1.1 Subject Disposition
 
	
 
Section 4.1.1 Subject Disposition Additional summary of the number and percentage of subjects who underwent the lactic acid sting test (Table 14.1.1).
 
The derivation for treatment duration has been added in the listing shell in Section 7 as well as in the text under section 4.1.1.
 
	
This information will be useful in the CSR to assess the disposition of subjects between onset of screening and randomisation.
 
 
While reviewing the draft CSR, it had been identified that the calculation of the treatment duration in Listing 16.2.1.1 was not correct (addition of 1 day was not added). No derivation had previously been provided in the RAP amendment.
 

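### SAP Addendum 1 keeps the statement that all adverse events will be summarised, but no planned table can show one arising between the lactic acid sting test and first product use

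*SAP*

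**What the plan says.** **Protocol.** Section 7.1.1 defines an AE to include untoward occurrences associated in time with the lactic acid procedure, and section 7.2 starts AE collection after that procedure. Section 9.2.1 sets the population to match: "The Safety population includes all subjects from the point of the lactic acid stinging test procedure until completion of the study". Section 9.3.4 has AEs tabulated by MedDRA term, with treatment-emergent summaries among the further outputs.

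**SAP Amendment 1.** Section 4.1.3 keeps the same set: "Comprises of all subjects for whom the lactic acid stinging test was performed". Section 7 indexes four AE tables, 14.3.1.1 to 14.3.1.4. All are treatment-emergent and all use the Safety population. No definition of treatment-emergent is given.

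**SAP Addendum 1.** Section 4.1.3 now requires randomisation and at least one application: "All subjects, for whom the lactic acid stinging test was performed, were randomized and had at least one study treatment application". On timing, section 1 says: "These changes were identified during CSR development, and hence were identified after unblinding but prior to final CSR". On the reason, Table 1 says: "However the safety population definition applied to the TFLs differed from the planned definition", and then that "the study team decided that the definition of the safety population and TEAE definition applied to the TFLs was the most appropriate". Section 4.6.1 defines treatment-emergent as onset at or after the first supervised use, classes anything earlier as non-treatment-emergent, and still states: "All adverse events (AEs) will be summarised by primary system organ class and preferred term according to the current version of the MedDRA". The addendum adds the number sting-tested to Table 14.1.1. It adds no AE table.

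**The concern.** A safety population fixed in the protocol was changed after unblinding, and the stated reason is that the programs had used a different one. The addendum acknowledges that the first intention was to report all AEs from the sting test onward. It does not say why AEs before product use should no longer be tabulated.

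AEs are a secondary endpoint (frequency and severity), and the sting test is a study procedure in which 10% lactic acid is applied to the face. If the outputs follow the addendum, the report will contain a general statement that its tables cannot honour. A reader who wants the frequency of AEs after the procedure will have to build it from line listings.

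**Working it through.** No sample-size or power figure is involved; the protocol says the sample size rests on clinical considerations. The check compares definitions with outputs and then bounds the number of women affected.

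**1. Definitions**

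| Source | Sting-tested | Randomised | At least one application |
|---|---|---|---|
| Protocol 9.2.1 | required | not required | not required |
| SAP Amendment 1, 4.1.3 | required | not required | not required |
| SAP Addendum 1, 4.1.3 | required | required | required |

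**2. Where an AE between the sting test and first use can appear**

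Visit 2 falls within 7 days of Visit 1, so the interval is up to 7 days.

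| Output | Untreated women | Treated women |
|---|---|---|
| Tables 14.3.1.1 to 14.3.1.4 | no | no |
| Listing 16.2.7.1 (randomised) | only if randomised | yes |
| Listing 16.2.7.2 (non-randomised) | yes | not applicable |
| Table 14.1.1, AE as reason for not being randomised | count only | not applicable |

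Of the four AE tables, none can include such an event. Both AE listings can.

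**3. Two mechanisms**

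- Untreated women leave through the change of population.
- Treated women stay in the Safety population, but their earlier events leave through the treatment-emergent rule combined with a table list that holds only treatment-emergent tables. That list predates the addendum.

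It follows that restoring the population alone would put no pre-product event into any table. A further table is needed as well.

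**4. Upper bound on women removed**

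Inputs, from protocol 9.1: up to 170 screened, about 92 randomised. Assumptions: everyone screened is sting-tested, and all 92 randomised women apply the product, the first use being supervised at Visit 2.

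Women removed = screened - 92; share = removed / screened.

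- 170 screened: 170 - 92 = 78; 78/170 = 45.9%
- 150 screened: 150 - 92 = 58; 58/150 = 38.7%
- 120 screened: 120 - 92 = 28; 28/120 = 23.3%

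The 120 and 150 are illustrative. The documents give no actual count of women screened or tested. The Visit 1 list puts the eligibility check before the sting test, and the addendum reports those tested as a percentage of those screened, so fewer than all may have been tested.

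**The case against.** The strongest reply is that the addendum largely brings the text into line with shells that already assumed a treated set. In Amendment 1 the Safety population was to follow the treatment actually received, which untreated women do not have. Table 14.1.1 expressed it as a percentage of those randomised. Listing 16.2.3.1 gave a yes/no Safety flag for randomised women only, yet a correctly enrolled randomised woman must have had the sting test and so could never be a no under the old definition. This stands: a treated set is the sensible basis for treatment-emergent tables by arm.

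It is also fair that the change and its reason are disclosed, that the study is non-comparative with no formal inference, and that the success criterion uses scores in the ITT population. Women who were never randomised belong to no arm, so removing them cannot favour a product. A reader might infer from the timing that the change was made to improve a result or to hide events; nothing in the documents supports that.

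A reader might also infer that early events go uncounted or that no denominator exists. That is not so. The two listings retain the events. Table 14.1.1 gives the number sting-tested and counts AEs recorded as the reason for not being randomised. That row gives no term and no class, however, and leaves out any AE that was not the reason.

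Finally, protocol 6.1.7 and 7.1.1 exclude responses gradable on the sting scale from the AE definition; only unusual reactions qualify. The added table would therefore not give a rate of ordinary stinging, and it may hold few events or none. That limits its yield. It does not make the retained statement in 4.6.1 achievable with the tables as planned.

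**Conclusion.** The point holds as a minor reporting correction. After unblinding, the protocol's Safety population was replaced by the programmed one, while a statement was retained that the planned tables cannot meet: no table gives the frequency, by class and term, of AEs between the sting test and first product use.

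It is tempting to blame the narrowed population for the whole gap. The documents do not bear that out, because for treated women the cause is the treatment-emergent restriction, whose table list was already in Amendment 1.

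The change removes at most 78 of 170 women from the Safety population, on the assumptions stated with the calculation. That is a ceiling on people, not on events. The documents do not show whether any AE occurred in the interval. Neither the ITT success criterion nor any reading of one product against the other is affected.

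**What to change.** - Keep the addendum's randomised-and-treated set for Tables 14.3.1.1 to 14.3.1.4, under a name of its own.
- Retain the protocol's Safety population (all sting-tested women) for one added table of non-treatment-emergent AEs by system organ class and preferred term. It should cover onset from the sting test to first product use or, for women not randomised, to screen failure. The denominator is the sting-tested count already in Table 14.1.1.
- State both denominators in the report, and say in the addendum which set each AE table uses.

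The cost is one table and a short paragraph. The table may be empty, and a stated zero with its denominator is still informative. The data should already be held: protocol 7.2 collects AEs from the sting test onward, and Listing 16.2.7.2 presupposes them for women not randomised. One thing to confirm first: the minimum screen-failure record in protocol 4.3 names only serious events, so the team should check that non-serious AEs were in fact captured for these women and footnote the table if they were not.
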